6.11.2 Efficacy Analysis

6.11.2.1 Proportion of subjects in renal response

The number of subjects that meet all four criteria in the above definition of renal response will be summarized by treatment group. The number of subjects who meet each of the four individual criteria will also be summarized by treatment group. These summaries will be presented for Months 6, 12, 18, 24, 30 and 36. Subjects who withdraw from the study prior to the response assessment will be defined as non-responders. The analysis of overall renal response and each of the components will be conducted on the ITT population using a logistic regression model with terms for treatment, baseline UPCR, biopsy class, MMF use at baseline and region, and renal response (Yes/No) at Months 6, 12, 18, 24, 30 and 36 as the response variable.

The results will be expressed as an odds ratio (and associated two sided- 95% confidence interval [CI]) for voclosporin compared to placebo. Odds ratios greater than unity will mean the odds of response are greater for voclosporin than for placebo and therefore indicate a benefit of the voclosporin treatment arm. The p-value of the treatment effect will also be reported.

The following SAS program will be used for the primary efficacy analysis:

```
proc logistic data = data;
class treatment_arm mmf_use biopsy_class region / param=glm;
model response = treatment_arm mmf_use biopsy_class baseline_upcr region;
run;
```

Listing of renal responders and non-responders will also be provided.

QMD Ref: [REDACTED]	Effective: 12Aug2019	Governing QMD: [REDACTED]
Confidentiality Statement		
This document is the property of [REDACTED] and may not be duplicated, copied, altered or removed from company without prior approval from [REDACTED] or in compliance with [REDACTED].		

REF: [REDACTED]

		Controlled Quality Management Document	
		Sponsor:	Aurinia Pharmaceuticals
		Protocol Number:	AUR-VCS-2016-02
STATISTICAL ANALYSIS PLAN. PHASE 2-3-4			

6.11.2.2 Proportion of subjects in partial renal response defined as a 50% reduction from baseline in UPCR

Change from baseline in UPCR will be calculated as the post baseline measurement minus the AURORA 1 baseline measurement. Percent change from baseline will be calculated as:

$$\text{Percent change from baseline (UPCR_pc)} = \left(\frac{\text{Change from baseline}}{\text{Baseline}} \right) \times 100$$

A 50% reduction in UPCR will be indicated by UPCR_pc <= -50. Subjects with missing UPCR values will be considered non-responders. This endpoint will be analyzed at Months 6, 12, 18, 24, 30 and 36, and presented similarly to the primary efficacy endpoint as described above. A listing of subjects considered partial responders will be provided.

This analysis will also be performed using the alternative baseline definition of the lowest UPCR value pre-dosing.

6.11.2.3 Renal flare and Extra-renal flare as adjudicated by the Clinical Endpoints Committee (CEC)

The proportion of subjects with renal and extra-renal flares (as adjudicated by the CEC) will be analyzed in a similar fashion to the proportion of subjects achieving response.

The ability for an individual subject to experience a flare depends on first achieving a given response. This response is a post randomization event and subsequent analysis and results can, therefore, be difficult to interpret. While the numbers of subjects with flares will be summarized, the main analysis will, in essence, be an analysis of ‘positive outcome’ vs ‘negative outcome’ including all subjects. A positive outcome will be defined as a subject with an initial response without a subsequent flare, while a negative outcome will be the absence of an initial response or a flare following initial response.

Both Renal flares and Extra-Renal flares will be summarized as described for Response Rate. Additionally, the frequency and percentage of both Renal flares and Extra-Renal flares will be summarized by year.

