### **13.8.2.2 Renal flare and Extra-renal flare**

The proportion of subjects with renal and extra-renal flares (as adjudicated by the CEC) will be analyzed in a similar fashion to the proportion of subjects achieving response.

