3.2 Secondary Endpoints

3.2.1 Key Secondary Endpoints

- Renal response at Months 12, 18, 24, 30 and 36. Estimand is the proportion of subjects showing renal response (programmed response) in the Intention-To-Treat (ITT) Population when comparing voclosporin and placebo at each visit. Renal response is defined as:
 - UPCR of ≤ 0.5 mg/mg
 - Estimated glomerular filtration rate (eGFR) ≥ 60 mL/min/1.73 m² or eGFR < 60 mL/min/1.73 m² with no confirmed decrease $> 20\%$ or eGFR < 60 mL/min/1.73 m² with confirmed decrease $> 20\%$ but with no disease-related or treatment-related eGFR associated AE present at time of assessment
 - Received no rescue medication for LN
 - Did not receive more than 10 mg prednisone for ≥ 3 consecutive days or for ≥ 7 days in total during the 8 weeks prior to the renal response assessment.
 - Subjects who withdraw from the study prior to the response assessment will be defined as non-responders.

QMD Ref: [REDACTED]	Effective: 12Aug2019	Governing QMD: [REDACTED]
Confidentiality Statement		
This document is the property of [REDACTED] and may not be duplicated, copied, altered or removed from company without prior approval from [REDACTED] or in compliance with [REDACTED].		
REF: [REDACTED]		Page 9 of 37

		Controlled Quality Management Document	
		Sponsor:	Aurinia Pharmaceuticals
		Protocol Number:	AUR-VCS-2016-02
STATISTICAL ANALYSIS PLAN. PHASE 2-3-4			

- Partial renal response at Months 12, 18, 24, 30 and 36 defined as a 50% reduction from baseline in UPCR. Estimand is the proportion of subjects showing partial renal response (programmed response) in the ITT Population when comparing voclosporin and placebo at each visit.
- Renal flare as adjudicated by the Clinical Endpoints Committee (CEC). Estimand is the proportion of subjects showing renal flare (CEC adjudicated response) in the ITT Population when comparing voclosporin and placebo at each visit.
- Extra-renal flare as adjudicated by the CEC. Estimand is the proportion of subjects showing extra-renal flare (CEC adjudicated response) in the ITT Population when comparing voclosporin and placebo at each visit.
- Safety of Estrogens in Lupus Erythematosus National Assessment- Systemic Lupus Erythematosus Disease Activity Index (SELENA-SLEDAI) scores by visit. Estimand is the mean change from AURORA 1 baseline in Total SELENA-SLEDAI score in the ITT Population when comparing voclosporin and placebo at each visit.

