6.11.1 Efficacy Endpoint

Renal response is defined as:

- UPCR of ≤ 0.5 mg/mg
- eGFR criteria:
 - eGFR ≥ 60 mL/min/1.73 m² or
 - eGFR < 60 mL/min/1.73 m² with no confirmed decrease $> 20\%$ or
 - eGFR < 60 mL/min/1.73 m² with confirmed decrease $> 20\%$ but with no disease-related or treatment-related eGFR associated AE present at time of assessment
- Received no rescue medication for LN
- Did not receive more than 10 mg prednisone for ≥ 3 consecutive days or for ≥ 7 days in total during the 8 weeks prior to the renal response assessment.

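### SAP 6.11.2.3 makes renal response without a later flare the main analysis for extra-renal flare, which is not the SAP 3.2.1 estimand and has no support in the documents

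*SAP*

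**What the plan says.** SAP 3.2.1 lists extra-renal flare as a key secondary endpoint in its own right: "Estimand is the proportion of subjects showing extra-renal flare (CEC adjudicated response) in the ITT Population", compared between arms at each visit. It sets no response condition. Protocol 13.8.2.2 agrees: "The proportion of subjects with renal and extra-renal flares (as adjudicated by the CEC) will be analyzed in a similar fashion" to response.

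SAP 6.11.2.3 has one heading for both flare types and opens with the same plan as the protocol. It then gives a reason for doing something else: "The ability for an individual subject to experience a flare depends on first achieving a given response". The consequence follows: "While the numbers of subjects with flares will be summarized, the main analysis will, in essence, be an analysis of" positive against negative outcome in all subjects. The definition is "A positive outcome will be defined as a subject with an initial response without a subsequent flare". A negative outcome is no initial response, or a flare after one. Extra-renal flare is not excepted.

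The section ends: "Both Renal flares and Extra-Renal flares will be summarized as described for Response Rate". It adds frequencies and percentages by year.

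The only responses the SAP defines are renal. SAP 6.11.1 begins "Renal response is defined as" and gives criteria on UPCR, eGFR, rescue medication and prednisone. SAP 6.11.2.2 defines partial renal response from UPCR alone. SAP Section 9, which lists changes from the protocol analysis, does not mention the composite.

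**The concern.** The composite and the estimand measure different things. A subject who never has an extra-renal flare but does not reach renal response counts as a negative outcome. A non-responder who does have an extra-renal flare is also negative, exactly as without the flare, so flares in non-responders cannot affect the result.

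If the arms differ in renal response, the main extra-renal comparison will favour the arm with more responders even when extra-renal flare is equally common in both. A reader of this key secondary endpoint would then take a renal result for an extra-renal one.

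Two gaps add to this. The initial response is not defined: full or partial, and at which of the assessed months. It is also unclear whether the closing sentence means a logistic model for flares themselves or only a table.

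**Working it through.** **Text.** Each item concerns extra-renal flare.

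| Source | Quantity | Response condition |
|---|---|---|
| SAP 3.2.1 | proportion of ITT subjects with flare | none |
| Protocol 13.8.2.2 | proportion with flare, analysed like response | none |
| SAP 6.11.2.3, opening | proportion with flare, analysed like response | none |
| SAP 6.11.2.3, main analysis | initial response and no later flare | yes; response not specified |

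Entry requires 52 completed weeks of AURORA 1 treatment, not renal response (Protocol 5.2), so non-responders can be in the ITT population. Neither document defines extra-renal flare or ties it to renal response.

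**Inputs.** The ITT population is 216 (SAP 6.1.1). The arm split is not given; 216/2 = 108 per arm is assumed. The documents give no response or flare rates, so all rates below are assumptions. The initial response is taken to be renal, as no other is defined.

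**Formulas.** Composite proportion = P(response) × (1 − flare risk in responders). OR = [a/(1−a)] / [b/(1−b)], with a for voclosporin and b for placebo. The interval is exp(ln OR ± 1.96 × SE), with SE² = 1/(108a) + 1/(108(1−a)) + 1/(108b) + 1/(108(1−b)). No covariate adjustment.

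**Equal 5% extra-renal flare, independent of response (flare OR 1.00).**

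| Response, voclosporin vs placebo | Composite a vs b | Composite OR (95% CI) |
|---|---|---|
| 50% vs 50% | 0.475 vs 0.475 | 1.00 (0.59 to 1.71) |
| 50% vs 40% | 0.475 vs 0.380 | 1.48 (0.86 to 2.54) |
| 60% vs 45% | 0.570 vs 0.4275 | 1.78 (1.04 to 3.04) |
| 70% vs 50% | 0.665 vs 0.475 | 2.19 (1.27 to 3.80) |

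For the last row: (0.665/0.335)/(0.475/0.525) = 1.985/0.905 = 2.19; ln OR = 0.786; SE = 0.2805. The renal response OR itself, 0.70 vs 0.50, is 2.33 (1.34 to 4.08), so the composite nearly repeats it. A 120/96 split changes the 2.19 interval only to 1.26 to 3.81.

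**Other equal flare rates, response 70% vs 50%.** At 2%, 0.686 vs 0.490 gives 2.27 (1.31 to 3.96). At 10%, 0.630 vs 0.450 gives 2.08 (1.21 to 3.59).

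**Flare not independent of response.** Keep response at 70% vs 50% and risk at 5% in responders, and set risk in non-responders to k × 5%. The composite stays at 2.19 by construction, because risk in non-responders does not enter it. The ITT flare OR does move:

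| k | ITT flare | Flare OR (95% CI) |
|---|---|---|
| 0 | 3.5% vs 2.5% | 1.41 (0.29 to 6.90) |
| 0.5 | 4.25% vs 3.75% | 1.14 (0.29 to 4.46) |
| 1 | 5% vs 5% | 1.00 (0.29 to 3.40) |
| 2 | 6.5% vs 7.5% | 0.86 (0.30 to 2.44) |
| 3 | 8% vs 10% | 0.78 (0.31 to 2.00) |

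The composite cannot tell these situations apart.

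**The direction can reverse.** With flare 20% on voclosporin vs 10% on placebo and response 60% vs 40%, the flare OR is 2.25 (1.03 to 4.94), which is harm. The composite is 0.60 × 0.80 = 0.48 vs 0.40 × 0.90 = 0.36, OR 1.64 (0.95 to 2.83), in the direction of benefit.

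**Renal flare, for contrast.** If only responders can flare, response 70% vs 50% with equal 10% risk gives ITT flare of 7% vs 5%, OR 1.43 (0.46 to 4.46), against the arm with better response. That is a fair motive for a composite there.

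**The case against.** - **Wording.** The composite paragraph speaks of a flare in general and never names extra-renal flare. It could be read as a rationale for renal flare only, with extra-renal flare analysed as a plain proportion under the opening sentence. On that reading an odds ratio for the SAP 3.2.1 estimand is already planned. The ambiguity is real. But the heading, opening and closing all cover both types, and the main analysis has no exception.
- **CEC charter.** The charter mentioned in Protocol Section 11 is not available and may tie extra-renal flare to a response. This stands as a limit: the dependence is unsupported here, not disproved. The mismatch between SAP 3.2.1 and 6.11.2.3 remains either way.
- **Assumed rates.** The distortion is nil when response is equal, and the interval at 50% vs 40% includes 1. If initial response means response at any time, rates could be high and close: 85% vs 80% with 5% flare gives 0.8075 vs 0.76, OR 1.32 (0.69 to 2.54). So the size is uncertain. The mechanism is not: in every case the composite follows renal response.
- **Importance.** This is one of several key secondary endpoints, the primary endpoint is safety, and flare counts by year stay visible. That limits the consequence, but does not make the main analysis answer its own estimand.

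**Conclusion.** The concern holds. Read as written, SAP 6.11.2.3 gives extra-renal flare a main analysis that differs from SAP 3.2.1 and Protocol 13.8.2.2, for a reason the documents do not support for that endpoint.

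Under the assumed rates with equal 5% flare, the composite odds ratio runs from 1.00 when response is equal to 2.19 when response is 70% vs 50%, while the flare odds ratio is 1.00 throughout. This rests on an assumed 108 per arm, unadjusted odds ratios, and reading the initial response as renal. The figures show direction and possible size; they do not predict the trial's result.

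This should be fixed before analysis, but it reaches no further than this endpoint. Using a composite for renal flare is a defensible trade-off and is not counted as an error.

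**What to change.** **Extra-renal flare.** Make the main analysis the proportion of all ITT subjects with at least one CEC-adjudicated extra-renal flare, using the same logistic model, and state the time window, since SAP 3.2.1 asks for a comparison at each visit. Do not apply the renal composite. State that an odds ratio below 1 favours voclosporin, because SAP 6.11.2.1 says the opposite for response: "Odds ratios greater than unity will mean the odds of response are greater for voclosporin than for placebo and therefore indicate a benefit". If the CEC charter does require a prior response, put that rule in the SAP.

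**Renal flare.** The composite may stay as the main analysis. Name it sustained renal response, define which response counts as initial and when, and say that the ITT renal-flare odds ratio is also reported.

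**Both.** Replace the closing reference to the response-rate summary with wording that says whether a model is fitted. Align SAP 3.2.1 with the result and list the change in Section 9.

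**Cost.** SAP wording and one or two tables from data already adjudicated. The drawback is few events. At an assumed 5% per arm there are about 11 (216 × 0.05 = 10.8), and an odds ratio of 1.00 has a 95% CI of 0.29 to 3.40 (0.15 to 6.72 at 2%; 0.41 to 2.43 at 10%). The five-term model may then fit poorly, so the SAP should name a fallback, for example an unadjusted odds ratio with an exact interval.

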6.11.2.4 Change from Baseline Endpoints

The following endpoints are included in change from baseline endpoints:

- Change in SELENA-SLEDAI scores from AURORA 1 baseline at Months 6, 12, 18, 24 and 36. Change from baseline in SELENA-SLEDAI total score will be the response

QMD Ref: [REDACTED]	Effective: 12Aug2019	Governing QMD: [REDACTED]
Confidentiality Statement		
This document is the property of [REDACTED] and may not be duplicated, copied, altered or removed from company without prior approval from [REDACTED] or in compliance with [REDACTED].		
REF: [REDACTED]		Page 25 of 37

		Controlled Quality Management Document	
		Sponsor:	Aurinia Pharmaceuticals
		Protocol Number:	AUR-VCS-2016-02
STATISTICAL ANALYSIS PLAN. PHASE 2-3-4			

variable in the Mixed Effect Model Repeated Measures (MMRM) model. The scores of the individual SELENA-SLEDAI items and the total score of each subject will be listed.

- Change in UPCR, eGFR, urine protein, and serum creatinine from AURORA 1 baseline at Months 6, 12, 15, 18, 21, 24, 27, 30, 33 and 36.
- Changes in eGFR between last on-treatment value and last off-treatment values will also be summarized.
- Change in immunology parameters (C3, C4, and anti-dsDNA) from AURORA 1 baseline at Months 6, 12, 15, 18, 21, 24, 27, 30, 33 and 36.
- Change in HRQoL (SF-36) from AURORA 1 baseline at Months 6, 12, 18, 24, 30, and 36. Only the scales (Physical functioning, Role limitations due to physical health, Role limitations due to emotional problems, Energy/fatigue, Emotional well-being, Social functioning, Pain, General health, Total Mean Score) will be summarized. MMRM will be performed only for Total Mean Score. The individual items and scales will be listed.

Change from baseline endpoints will be summarized using descriptive statistics for observed values and changes from baseline by treatment group. All data will be listed.

Change from baseline will be analyzed using a MMRM analysis with treatment arm, visit, treatment by visit interaction, biopsy class, MMF use at baseline, region and baseline value included as a covariates in the model. Results will be expressed as differences between treatment arms (along with the associated 95% CI). The observed and change from baseline values will be summarized by treatment visit and treatment arms. The Least Squares (LS) means and their corresponding 95% CI of the change from baseline values will also be presented for each visit and for the overall change. The model will be fitted using an unstructured (UN) covariance matrix. Should the UN covariance matrix not converge, then an autoregressive (AR(1)) covariance matrix will be used. The covariance matrix used will be indicated in the footnotes. The Kenward-Roger degree of freedom adjustment will be applied. LS mean plots of mean change from baseline versus visit will be presented for UPCR and eGFR.

QMD Ref: [REDACTED]	Effective: 12Aug2019	Governing QMD: [REDACTED]
Confidentiality Statement		
This document is the property of [REDACTED] and may not be duplicated, copied, altered or removed from company without prior approval from [REDACTED] or in compliance with [REDACTED].		

REF: [REDACTED]

		Controlled Quality Management Document	
		Sponsor:	Aurinia Pharmaceuticals
		Protocol Number:	AUR-VCS-2016-02
STATISTICAL ANALYSIS PLAN. PHASE 2-3-4			

The SAS code anticipated to be used for analysis of the change from baseline endpoints is as follows:

```
proc mixed data=dataset;
class subject treatment visit biopsy class mmf use region;
model response = treatment visit treatment*visit biopsy_class mmf_use region
baseline / ddfm=kr
repeated visit / subject=subject type=un r corr;
lsmeans visit*treatment / pdiff cl e;
run;
```

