6.1 Analysis Populations

6.1.1 Intent-to-Treat Population

The ITT population will be based on ITT principles and will consist of all subjects who are consented to treatment in AURORA 2 (n=216). This group will be analyzed based on the treatment to which the subject was randomized in the AURORA 1 study.

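### The MMRM assumes the same baseline slope at every visit from Month 6 to Month 36; adding a baseline-by-visit term is a small, nearly free improvement

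*SAP*

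**What the plan says.** SAP 6.11.2.4 lists the fixed effects as treatment, visit, their interaction, biopsy class, MMF use, "region and baseline value included as a covariates in the model". The SAS code agrees. It reads "model response = treatment visit treatment*visit biopsy_class mmf_use region" and continues on the next line with "baseline / ddfm=kr". Baseline appears once, and only treatment is crossed with visit.

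UPCR, eGFR, urine protein, serum creatinine, C3, C4 and anti-dsDNA are modelled as change from AURORA 1 "baseline at Months 6, 12, 15, 18, 21, 24, 27, 30, 33 and 36", which is 10 visits. The SF-36 total score has six visits (Months 6, 12, 18, 24, 30, 36). SELENA-SLEDAI has five: "Change in SELENA-SLEDAI scores from AURORA 1 baseline at Months 6, 12, 18, 24 and 36".

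On covariance: "The model will be fitted using an unstructured (UN) covariance matrix". If that does not converge, "then an autoregressive (AR(1)) covariance matrix will be used".

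Protocol 13.8.2.3 has the same single baseline term. SAP section 9 adds biopsy class, MMF use and region to the protocol's model, but no baseline-by-visit term. SAP 3.2.1 and 3.2.2 define the mean-change estimands at each visit. SAP 6.11.4 plans no sensitivity analysis.

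**The concern.** A value measured before AURORA 1 dosing may predict Month 6 better than Month 36. If so, one common slope adjusts too little at one end of follow-up and too much at the other. Because the estimands are visit-specific, any loss falls on results that will be reported, Month 36 among them.

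Two things could follow. Standard errors at the end visits could be larger than they need be. And if the arms differ at baseline, the difference would be only partly removed at those visits. The second matters because AURORA 2 holds 216 of the 356 treated AURORA 1 subjects (SAP 6.1.1, 6.1.2). They were selected after randomization, by completing 52 weeks and by the investigator's view that treatment should continue (protocol 5.2), so balance is not guaranteed.

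**Working it through.** **Inputs from the documents.** N=216 (and 356 - 140 = 216); the visit schedule; unstructured covariance; two-sided 5% level. There is no plan figure to reproduce: SAP section 4 has no sample size calculation, and no SD, power or baseline-outcome correlation is given.

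**Assumptions.** Baseline and each visit value scaled to SD 1; 108 subjects per arm; baseline correlation falling linearly in months from Month 6 to Month 36; correlation of 0.70, 0.85 or 0.95 between residuals three months apart. Modelling change instead of the raw value shifts every slope by the same amount, so it does not affect the comparison.

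**Formula.** Let b be the vector of true slopes by visit and S the residual covariance. The fitted common slope tends to

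c = (1'S⁻¹b) / (1'S⁻¹1).

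Relative to a model with `baseline*visit`, the standard error at visit t is multiplied by

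√(1 + (b_t - c)² / S_tt).

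**Worked case.** Correlation 0.5 to 0.1, three-month correlation 0.85, c = 0.329:

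- Month 6: S = 1 - 0.5² = 0.75; (0.5 - 0.329)² / 0.75 = 0.039; factor 1.019.
- Month 36: S = 1 - 0.1² = 0.99; (0.1 - 0.329)² / 0.99 = 0.053; factor 1.026.

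**Range over the three between-visit correlations.**

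| Baseline correlation, Month 6 to 36 | SE factor, Month 6 | Month 24 | Month 36 | Overall change |
|---|---|---|---|---|
| 0.4 to 0.4 | 1.000 | 1.000 | 1.000 | 1.000 |
| 0.5 to 0.3 | 1.004-1.006 | 1.000-1.001 | 1.006-1.008 | 1.000-1.001 |
| 0.5 to 0.1 | 1.012-1.022 | 1.002-1.006 | 1.024-1.036 | 1.002-1.005 |
| 0.7 to 0.1 (extreme) | 1.005-1.051 | 1.009-1.047 | 1.067-1.134 | 1.013-1.046 |

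For scale, a Month 36 comparison with 80% power would have about 79% in the second row and 77-78% in the third.

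**Baseline imbalance.** The bias left at visit t is (b_t - c) times the imbalance. In the worked case a 0.2 SD imbalance leaves 0.2 × 0.171 = 0.034 SD at Month 6 and 0.2 × (-0.229) = -0.046 SD at Month 36. Chance imbalance is already counted in the SE factors above; only a systematic imbalance is extra.

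**Simulation check.** 300 runs, N=216, 10 visits, unstructured covariance, no true effect, correlation 0.5 to 0.1, three-month correlation 0.85:

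- Complete data, balanced arms: Month 36 model SE 0.139 with one slope and 0.136 with the interaction (ratio 1.026, as the formula gives). Rejection was 5.0% and 3.7%.
- About 30% dropout depending on earlier outcomes, and on baseline in one arm: SE 0.162 against 0.157; bias 0.016 against -0.002 SD; rejection 7.0% against 6.0%.
- The same dropout plus a 0.2 SD baseline imbalance: one-slope bias +0.031 SD at Month 6 and -0.035 SD at Month 36, against 0.001 and -0.005 with the interaction.

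Monte Carlo error is about 0.01 SD for bias and 1.3 points for rejection.

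**Cost of the extra slopes.** √(1 + 1/(216 - 4)) = 1.002 per visit.

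**The case against.** The strongest reply is that this is a modelling preference. Protocol, SAP text and SAS code agree, and the model can be fitted as written. The endpoints are secondary in a study whose primary objective is safety. Observed values and changes by visit and arm are reported as well. All of that stands.

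It also stands that an unstructured covariance lets the variance differ by visit and so absorbs the misfit. With complete data and balanced baselines the treatment differences are unbiased and their standard errors valid; the simulated 5.0% rejection rate is consistent with this.

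A reader might infer more: that the baseline adjustment is wrong as planned, that precision is certainly being lost, or that the handling of missing data is invalid. The documents do not support these readings. They contain no correlation between baseline and later values, so a weakening relation is an assumption, and with equal slopes the loss is exactly zero. The 13% loss at Month 36 arises only in the extreme assumed case. The dropout bias of 0.016 SD is under two Monte Carlo errors and rests on an assumed dropout rate and mechanism.

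What the reply lacks is a drawback of the extra term. The AR(1) fallback would offer less protection, since its single variance cannot absorb misfit at particular visits; this is reasoned, not simulated.

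**Conclusion.** The concern holds as a low-severity improvement, not as an error. The plan makes an equal-slopes assumption that it neither states nor checks. If slopes differ by visit, the cost is a slight loss of precision at the first and last visits and incomplete adjustment there for any baseline imbalance. All sizes rest on the assumed correlations, linear decline and equal arms. The dropout and imbalance results also rest on an assumed 30% dropout and a 0.2 SD imbalance; the documents supply none of these.

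**What to change.** In SAP 6.11.2.4, add the baseline-by-visit interaction to the list of model terms and `baseline*visit` to the PROC MIXED model statement, and record it in section 9 beside the other added covariates. If the sponsor prefers to keep the present model as the main analysis, the interaction model can be pre-specified as a sensitivity analysis under 6.11.4.

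The extra parameters are one fewer than the number of visits: 9 for the 10-visit endpoints, 5 for the SF-36 total score and 4 for SELENA-SLEDAI. At N=216 the price is about 0.2% in standard error. No additional data are needed.
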